
PROJECT TITLE
	
Pain outcomes after posterior capsular injection during Anterior Cruciate Ligament (ACL) reconstruction: A prospective, randomized trial.

BACKGROUND and RELEVANT REFERENCES
	
Post-operative pain control following elective anterior cruciate ligament reconstruction continues to be a hurdle for orthopaedic surgeons. This obstacle becomes particularly problematic during the first 36 hours after the operation, when the patient is experiencing pain at its peak intensity. Good control of pain leads to better patient comfort, confidence to place weight on the operative limb and improved ability to perform critical exercises in this period to improve joint range of motion. (Rev Bras Ortop. 2015 Jun 16;50(3):300-4)
 
A variety of anesthetic techniques have been employed to reduce pain including: cryotherapy, systemic analgesic and anti-inflammatory drugs, intrathecal, regional blockade of peripheral nerves and frequently intra-articular injections. Each technique has been studied at length with mixed but overall favorable results. However, in the authors' experience, after femoral nerve blockade, patients continue to complain of posterior knee pain in the Post-Anesthesia Care Unit (PACU) and peri-operative period. Intra-articular injections comprised of morphine and other Na-channel blocker analgesics may curb some of this pain by bathing the posterior capsule in anesthetic. However, there is still a large concern amongst orthopaedic surgeons about the potential harm these agents may have on the knee's healthy articular cartilage surfaces. The long term effects, including chondrolysis have been documented in the shoulder and while in the short term this effect is diminished there is still hesitation among surgeons to use this form of pain blockade.
 
This has led the authors to adapt a technique of isolated posterior capsular injections after total knee replacements from the joint arthroplasty literature, which has shown favorable results with low complication risk. (Orthop Clin North Am. 2015 Jan;46(1):1-8). We plan to study the effectiveness of this technique during ACL reconstruction in an attempt to curb the amount of posterior knee pain and decrease the overall narcotic use postoperatively while limiting the exposure of the native cartilage to harmful agents.
 
References: See Attached Sheet


OBJECTIVE
	
To determine if there is a significant difference in post-operative pain visual analog pain (VAS) scores, a decrease in time before first narcotic and total decrease in peri-operative narcotic use after ACL bone-patellar-bone reconstruction after a posterior capsular injection with 20cc of 0.5% marcaine.

SITE/RESOURCES Please list location where study will be carried out and any staffing resources that will be needed. Indicate if site/staff have committed to project or if they have been approached
	
Kerlan Jobe Orthopaedic Clinic
 
Post-Anesthesia Care Unit Nursing staff: if the fellow is unavailable they will deliver the visual analog pain scale survey to patients at specific time points. – Staff has been instructed on how to administer the surveys appropriately.
 
Anesthesia- We have discussed with the anesthesia staff that the femoral nerve blocks will be standardized for all patients in the study.
 
Statistician – Cedars STATs department has been contacted


METHODOLOGY To include: -hypothesis - variables - methods -statistical analysis plan - power analysis
	
Hypothesis: Patients who receive a posterior capsular injection with Marcaine 0.5% during ACLR will report less pain and have less total narcotic use immediately post-op and up 4 days postoperatively compared to those that did not receive this injection.
 
Variables
 
 
1) Injection Group       
 
a. VAS Scores @ 15min/1 hour/POD1- 4
 
b. Time to first narcotic
 
c. Total narcotic use
 
d. 3 month Post-op visit assessment ((rule out chondrolysis)
 
 
 
2) Non-Injection Group       
 
a. VAS Scores @ 15min/1 hour/POD 1-4
 
b. Time to first narcotic
 
c. Total narcotic use
 
d. 3 month Post-op visit assessment (rule out chondrolysis)
 
 
 
 
Methods A prospective series of consecutive patients undergoing primary ACLR will be recruited from a preoperative log of patients seeing one of four sports medicine fellowship trained surgeons within our group. Patients undergoing primary unilateral anterior cruciate ligament reconstruction (ACLR) either with bone-patellar bone autograft or Achilles tendon allograft will be included by surgeons using similar techniques and fixation options.
 
Inclusion Criteria – Adult individuals (ages 18-60), both sexes, submitted to elective ACL reconstructions with or without partial menisectomies of the medial or lateral meniscus.
 
Exclusion Criteria – 1) Multiligamentous injury or revision surgery 2) Known narcotic/substance abuse or regular opiate use 3) Known allergy to any medication or anesthetic being used in this study 4) Patients with pre-existing diabetic or femoral neuropathy 5) INTRAOPERATIVELY- if chondral microfractures, inside-out or outside-in meniscal repairs were performed (***)Since these additional surgeries within the joint may increase the perceived level of pain post-op(***)
 
After consenting to participate, subjects will be randomized into one of two groups. Using a random number generator,

<http://stattrek.com/statistics/random-number-generator.aspx>

60 consecutively enrolled patients will be placed in their appropriate study arm. (Odd numbers = Control Group) (Even numbers = Experimental Group). Only the patient will be blinded to which arm of the study they belong.

Group 1(Control) patients will undergo routine arthroscopically assisted ACLR surgery with a standardized postoperative protocol. Group 2 (Experimental) patients will undergo the same procedure with the same postoperative protocols as Group 1, with the addition of the posterior capsular injection of 20 cc of Marcaine 0.5%. There are no placebo treatments being offered and the surgeons and operating room staff are not blinded to the subjects group. Injecting marcaine in this study will be performed in accordance with its standard use according to the FDA labeling/guidelines. The physicians will use their discretion as to the appropriate location for the injection into the posterior capsule of the knee which should bring no additional risks than expected for a knee injection.

At the conclusion of the case, each patient will receive a dry sterile dressing, followed by a compressive wrap and a hinged knee brace locked in extension. No drains, pain pumps or nerve stimulators will be used. The nurses in the recovery room who will be administering the VAS assessment and recording time and frequency of pain medication dosing will be blinded to the patients' Group number. The nurses will provide pain medications and the visual analog assessment for their duties in the post-op anesthesia unit, and are not administering drugs or procedures specifically for research purposes.

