#### *Post-operative Care*

All patients will be discharged home from the surgery center on the same day (within 2-3 hours) postoperatively. Patients will be made weight bearing as tolerated with crutches and a brace.

While in the PACU, at time points 15min and 1 hour, a standardized and previously validated visual analog scale (VAS) for pain assessment will be delivered to the patient by the recovery room nurse. In addition, during this time, the extent of postoperative motor block will be assessed using the Bromage scale as follows: 0 = free movement of the leg/foot, 1 = Free foot movement with only knee flexion 2 = Free foot movement with inability to flex knee and 3 = complete motor blockade of knee and foot.

Patients after discharge will then be asked to rate their most severe pain each morning and night for 4 consecutive postoperative days using this VAS pain scale. A standardized pain medication regimen will be given including: one or two tabs of Percocet 7.5/325mg to be taken every 4 to 6 hours as needed. A log of the time and amount of medication taken each POD will be kept and recorded by the patients. Patients will also be instructed to use cryotherapy for 20 min intervals 3 times per day. Patients will also begin on POD 0 the use of continuous passive motion machines starting at a comfortable range of motion and progressing 5 degrees/day as tolerated. Patients will return for their first post-operative visit between 7-10 days where diaries will be collected and the patient clinically assessed.

Patient's will also be seen at their three month post-operative visit and be clinically assessed for the presence of chondrolysis (a frequently measured

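### The protocol makes the fellow, whose blinding is never stated, first in line to deliver the recovery-room pain scale, while its procedural text assigns this to blinded nurses and also says only the patient is blinded

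*Protocol*

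**What the plan says.** Three places in the protocol deal with who hands the pain scale to the patient in the recovery room.

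- **Site/Resources**, on the PACU nursing staff: "if the fellow is unavailable they will deliver the visual analog pain scale survey to patients at specific time points". The nurse is the back-up and the fellow comes first.
- **Methodology, Methods**: "The nurses in the recovery room who will be administering the VAS assessment and recording time and frequency of pain medication dosing will be blinded". There is no mention of a fellow.
- **Post-operative Care**: at 15 minutes and 1 hour the form "will be delivered to the patient by the recovery room nurse". Again no fellow is mentioned, and this section does not speak of blinding.

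Three statements, all in Methods, deal with who is blinded.

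- The general statement: "Only the patient will be blinded to which arm of the study they belong".
- On those who know the arm: "the surgeons and operating room staff are not blinded to the subjects group". The same paragraph says that no placebo treatment is given.
- On the recovery-room nurses: they "will be blinded to the patients' Group number".

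The fellow is mentioned only in Site/Resources, and no blinding statement names that role.

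**The concern.** Pain on a VAS is subjective, and the control arm has no sham injection. Blinding the nurse who delivers the form is therefore the staff-side protection that the protocol describes for the PACU scores, although it does not use that word. Site/Resources, followed as written, replaces that nurse by default with someone whom no sentence blinds. Some early scores would then be collected by a blinded nurse and others by a person who may know the arm, depending on who is free.

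The second conflict is separate. If the general statement that only the patient is blinded governs, the nurses may know the arm too. Besides delivering the VAS, they give pain medication in the PACU and record when and how often it is given. The PACU part of the narcotic outcomes would then also be open to influence.

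The 15-minute and 1-hour scores are the VAS evidence for the immediate post-operative part of the hypothesis. Narcotic use is the other component of that part.

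**Working it through.** **Step 1. Set the passages side by side.**

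| Question | Site/Resources | Methods | Post-operative Care |
|---|---|---|---|
| Who delivers the PACU VAS? | Fellow; nurse only as back-up | Recovery-room nurses | Recovery-room nurse |
| Is that person blinded? | Not stated | Nurses blinded, but also only the patient blinded | Not stated |

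Staff cannot follow the first column and the other two together. Within Methods, the two blinding statements cannot both be true.

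**Step 2. Count the exposed scores.** Two VAS ratings are taken in the PACU. After discharge patients "rate their most severe pain each morning and night for 4 consecutive postoperative days", which gives 2 × 4 = 8 diary ratings. The total is 2 + 8 = 10, so 2/10 = 20% are directly exposed. The 8 diary ratings are affected only if the patient learns the arm.

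**Step 3. Reproduce the plan's own figure.** The Power Analysis gives a difference of 2, SD 2.5, two-sided alpha 0.05 and 80% power with 26 per group. With d = 2/2.5 = 0.8, the noncentral-t calculation gives n = 25.52, rounded up to 26, with power 0.807. The stated figure reproduces and is not in dispute. It supplies the SD used next.

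**Step 4. Illustrate the possible size.** From the documents: SD 2.5, 60 patients, alpha 0.05 two-sided. Assumed: 30 per arm; a fraction f of scores collected by the fellow; and a shift of b points in the injection arm's fellow-collected scores only. With no true effect:

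- average shift between arms = f × b
- standardised shift d = f × b / 2.5
- noncentrality = d × √(30/2), df = 30 + 30 − 2 = 58
- false-positive rate = probability that the two-sided t-test rejects

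| Share collected by the fellow (f) | b = 0.25 | b = 0.5 | b = 1.0 |
|---|---|---|---|
| 25% | 5.1% | 5.4% | 6.7% |
| 50% | 5.4% | 6.7% | 11.9% |
| 100% | 6.7% | 11.9% | 33.2% |

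For example, f = 0.5 and b = 1.0 give an average shift of 0.5, d = 0.2, noncentrality 0.2 × 3.873 = 0.775, and a rejection rate of 11.9%.

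A simulation of 100,000 trials, with the shift applied to a random half of the injection-arm scores, gave 5.5%, 6.6% and 11.7% for b = 0.25, 0.5 and 1.0. This agrees with the 50% row.

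**The case against.** The strongest reply is that the operative text largely settles the matter. The Site/Resources entry answers a form field about staffing, while the two procedural sections agree on the nurse. The general blinding sentence can be read as loose drafting, since the sentences after it say specifically who is and who is not blinded.

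Harm also needs a chain of conditions. Site/Resources must be the text that is followed, the fellow must know the arm, the fellow must cue the patient or disclose it, and a blinded patient's own rating must move. The last three are not documented. Only 2 of 10 ratings are exposed, and the Site/Resources clause covers VAS delivery, not medication recording. No document figure supports the assumed shifts or shares. The illustration uses a t-test, as the Power Analysis does, whereas the Statistical Analysis section plans Mann-Whitney for numeric variables.

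Most of this stands as a limit on size. It is correct that no bias has been shown, that the fellow's knowledge of the arm is unknown, and that the illustration cannot say which scenario applies. It does not remove the conflicts. The Site/Resources entry states an order of responsibility and adds that staff have been instructed in giving the survey, so it can be read as a working rule. Nothing in the protocol says which text takes precedence. Who collects an outcome and who is blinded are conduct rules that site staff take from the protocol, not details to be left to an analysis plan.

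**Conclusion.** The concern holds. The protocol is wrong as written on two points: it gives two incompatible rules for who delivers the PACU VAS, and two incompatible statements on whether the nurses are blinded. Both follow from the text alone, so confidence in them is high.

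The resulting bias is of unknown size. Under the stated assumptions it is negligible to modest unless the fellow collects most of the scores and the shift is large. The 33.2% figure needs every score to be fellow-collected and a full 1-point shift in one arm only. Exposure from the delivery conflict is limited to the 15-minute and 1-hour VAS. It depends on the fellow knowing the arm, which the documents neither state nor rule out. The point should be fixed because the trial has no placebo, the outcome is subjective and the correction costs almost nothing.

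**What to change.** Make two edits.

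1. In Site/Resources, remove the clause about the fellow. State that PACU nursing staff, blinded to group, deliver the VAS at 15 minutes and 1 hour. The entry then agrees with Methods and Post-operative Care.
2. In Methods, replace the general blinding sentence with one stating that the patient and the PACU nurses are blinded. Keep the existing statement that surgeons and operating room staff are not.

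If the sponsor wants to keep the fellow as a collector, the protocol must say so in all three places, state whether the fellow is blinded and, if so, how that is maintained.

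The cost of the two edits is the loss of the fellow as a collector. No extra staff are needed, because the nurses have already been instructed and do this assessment as part of their duties. Sample size, power and alpha do not change.

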	
outcome during knee pain medication injection studies).
 
Statistical Analysis Based on previous studies, the Mann-Whitney U test will check differences between numeric variables. Nonparametric Kruskal-Wallis tests can compare the analgesia level in the two groups and if possible ANOVA test can compare the analgesia duration. Chi-square tests will be utilized for any potential complications which will also be recorded. (J Inj Violence Res. 2013 Jun; 5(2): 84-88.) (Acta Ortop Bras. 2012;20(5); 285-90)
 
Power Analysis Prelim Power Analysis per STATS department @ Cedars: sample sizes of 26 for each group (N1=N2=26) = Total 52 patients to achieve 80% power to reject the null hypothesis of equal means when the population mean difference is 2 with a standard deviation for both groups of 2.5 and with a significance level (alpha) of 0.050 using a two-sided two-sample equal-variance t-test. A total of 60 patients will be enrolled to ensure we achieve adequate power for the study.

CLINICAL RELEVANCE IMPACT
	
Despite the addition of selective regional blockade by the anesthesia team including femoral and saphenous nerve blocks, a portion of patients are still experiencing post-operative knee pain within the first few hours to days after the procedure. Pain may be a result of the femoral tunnel drilling which theoretically may be relieved by a posterior capsular injection. Eliminating this painful period will improve the patient’s subjective experience undergoing surgery, and may also allow for earlier range of motion and participation in rehabilitation strengthening exercises performed by the patient in the peri-operative period.

APPROX BUDGET Include comprehensive and detailed budget. Do NOT include any overhead expenses
	
Marcaine 0.5% with epi & 20 cc, syringe = Pending Paper VAS forms = Pending (< \$100) Envelopes for randomization process = Pending (\$<50) Statistician = Pending

AUTHORS indicate areas of involvement
	
1. _[name] – Primary Researcher  2. _[name] – Principle Investigator  3. _[name].  4. _[name]. 
 
1= idea development/project design; 2=data collection; 3=data analysis; 4=data interpretation; 5=manuscript preparation/revisions

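### No pain rating is taken before surgery, so the VAS comparisons cannot be adjusted for starting pain: a missed gain in precision that is cheap to recover, not a bias

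*Protocol*

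**What the plan says.** Under Methodology, Variables, items 1a and 2a list the pain ratings for the two groups. Item 1a reads "VAS Scores @ 15min/1 hour/POD1- 4", and item 2a gives the same times. Post-operative Care places the 15-minute and 1-hour ratings in the recovery unit. After discharge, patients are asked to "rate their most severe pain each morning and night for 4 consecutive postoperative days using this VAS pain scale". No section names a pain rating before surgery.

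Patients can be reached beforehand: they "will be recruited from a preoperative log of patients", and "After consenting to participate, subjects will be randomized into one of two groups".

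Under Statistical Analysis, "the Mann-Whitney U test will check differences between numeric variables", and no covariate is named. The Power Analysis uses a two-sided, equal-variance two-sample t-test with "population mean difference is 2 with a standard deviation for both groups of 2.5 and with a significance level (alpha) of 0.050". It arrives at 26 per group (52 in total) for 80% power, with 60 to be enrolled.

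**The concern.** Patients differ in how much their knee hurts before the operation and in how they use a pain scale. Whatever part of this carries over into the post-operative ratings adds to their spread, and so to the SD of 2.5 used for sizing. A pre-treatment rating is the usual way to take some of it out. It also lets the reader see whether the arms started level.

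The protocol describes allocation by odd or even random number and mentions no stratification. It admits two graft types, four surgeons, ages 18 to 60, and patients with or without partial meniscectomy. With about 30 per arm, some chance imbalance in starting pain is quite possible.

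Most questions about the analysis model can wait for a statistical analysis plan, which may exist but is not shown. This one cannot, because the data collection schedule settles it. If the rating is not taken before surgery, no later document can adjust for it.

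**Working it through.** **Inputs from the protocol (Power Analysis).** Difference 2, SD 2.5 in each group, two-sided alpha 0.05, 26 per group, 60 enrolled. The section does not name the outcome; I take it to be VAS pain, the first outcome in the Objective.

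**Assumed input.** The correlation r between pre- and post-operative VAS is not in the protocol. I show r = 0.1 to 0.5.

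**Step 1: reproduce the stated sample size.** The standard error is SD × √(2/n) = 2.5 × √(2/26) = 0.693. The noncentrality is 2/0.693 = 2.88 on 50 degrees of freedom. Exact t-test power is 80.7% at 26 per group and 79.1% at 25. So 26 is the smallest size reaching 80%, and the stated figure is right. At 30 per arm (all 60 analysed, split equally) power is 86.1%.

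**Step 2: add a pre-operative VAS as a covariate.** The residual SD is 2.5 × √(1 − r²), so the share of variance removed is r². One degree of freedom is lost. For r = 0.3, the residual SD is 2.5 × √0.91 = 2.385, the standard error at 26 per arm is 0.661, and the noncentrality is 2/0.661 = 3.02 on 49 degrees of freedom, giving power of 84.2%.

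| Assumed r | Variance removed | Residual SD | Power, 26 per arm | Power, 30 per arm | n per arm for 80% |
|---|---|---|---|---|---|
| no covariate | – | 2.500 | 80.7% | 86.1% | 26 |
| 0.1 | 1% | 2.487 | 81.1% | 86.5% | 26 |
| 0.2 | 4% | 2.449 | 82.3% | 87.5% | 25 |
| 0.3 | 9% | 2.385 | 84.2% | 89.1% | 24 |
| 0.4 | 16% | 2.291 | 87.0% | 91.4% | 22 |
| 0.5 | 25% | 2.165 | 90.4% | 94.0% | 20 |

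**Step 3: check the alternative of change scores.** With equal SDs before and after, a change score has SD 2.5 × √(2(1 − r)). At r = 0.3 this is 2.958, and power at 26 per arm falls to 66.7%, below the unadjusted 80.7%. Change scores only break even at r = 0.5. The rating helps as a covariate; subtracting it could do harm.

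**Step 4: how likely is a visible imbalance?** The difference between arms in mean starting pain, in SD units, has standard error √(2/n): 0.277 at 26 per arm and 0.258 at 30. By the normal approximation, a difference of at least 0.3 SD in either direction has probability of about 28% and 25% respectively. Its effect on the result is scaled by r. At r = 0.3 and an outcome SD of 2.5, a 0.3 SD imbalance shifts the VAS difference by 0.3 × 0.3 × 2.5 = 0.225 points, about a third of the standard error of 0.693.

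**The case against.** The strongest reply is that nothing stated in the protocol is wrong. The trial is sized on the unadjusted SD and reaches its 80% without a baseline, with a margin if most of the 60 are analysed. That stands.

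The size of the gain rests wholly on an unknown correlation. Pain before elective surgery is not the same thing as acute surgical pain under a femoral block, or as the worst pain of a day at home. The correlation may be small and may differ by time point; at 0.1 the gain is under half a percentage point. The table also compares a t-test with a normal-theory adjusted model, whereas the planned test is Mann-Whitney, so the figures only indicate the likely gain. All of this stands too.

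A reader might infer four stronger things, none of which the protocol supports:

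- **That the result would be biased.** Patients are randomized, so the unadjusted comparison is unbiased in expectation, and chance imbalance is already allowed for in the p-value and confidence interval.
- **That the sample size is too small.** Step 1 shows that it is correct.
- **That one form would remove the differences between patients.** It removes only r² of the variance: 1% to 25% over the range shown.
- **That no adjusted analysis is possible.** Age, sex, graft type and surgeon could still serve as covariates. Only adjustment for starting pain is ruled out.

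The objection does not remove the core point: the rating is absent, it can be obtained only before surgery, and patients are identified and give consent beforehand.

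**Conclusion.** The point holds as a missed gain in precision. The VAS comparisons cannot be adjusted for starting pain, and balance between the arms in starting pain cannot be shown. The gain at 26 per arm runs from 0.4 percentage points of power at r = 0.1 (81.1% against 80.7%) to 9.7 points at r = 0.5 (90.4%). At 30 per arm it runs from 0.4 to 7.9 points above 86.1%.

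These figures assume a linear relation between the two ratings, the protocol's difference and SD, and equal arms. The correlation is assumed throughout. This is a minor and optional improvement; neither the validity of the comparison nor the stated sample size is in question.

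**What to change.** Add one pre-operative VAS to items 1a and 2a, on the same paper form, after consent and before the nerve block. Taking it before randomization is best, so that the rating cannot be influenced by allocation.

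Prespecify it as a covariate in the VAS analysis, in place of or alongside the Mann-Whitney test. ANCOVA, rank ANCOVA or a proportional-odds model with arm and pre-operative VAS would each serve. Do not analyse change from baseline. The form alone changes nothing unless the analysis uses it.

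The cost is one more form per patient and one more term in the model. The paper forms are already a budget line, put at under $100. The nurses described as instructed in giving the scale work in the recovery unit, so someone must be named to hand it out before surgery. If the correlation turns out low, the gain in power will be slight, and the main return will be a visible check on balance.

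### About 30 injected patients cannot rule out chondrolysis: a zero count bounds the three-month risk only at about 10–12%, and the stated chi-square test fails if neither arm has a case

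*Protocol*

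**What the plan says.** In the protocol's METHODOLOGY section, under Variables, item 1d for the injection group reads "3 month Post-op visit assessment ((rule out chondrolysis". Item 2d gives the non-injection group the same visit and purpose. The Post-operative Care section describes the visit more neutrally: "Patient's will also be seen at their three month post-operative visit and be clinically assessed for the presence of chondrolysis". It adds that this outcome is often measured in studies of knee injections. No case definition is given and no later visit is mentioned.

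The number injected follows from two statements. The Power Analysis says "A total of 60 patients will be enrolled to ensure we achieve adequate power for the study", and the Methods allocate patients by a random number generator ("Odd numbers = Control Group) (Even numbers = Experimental Group"). The sample size is justified on a difference in means alone: "sample sizes of 26 for each group (N1=N2=26) = Total 52 patients to achieve 80% power". No chondrolysis rate to be detected or excluded appears anywhere.

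The Statistical Analysis paragraph says that complications will be recorded and examined with chi-square tests. It does not name chondrolysis, but no other stated analysis could cover it.

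**The concern.** To rule out a harm is to show that it is absent, or at least that its rate lies below some acceptable value. The protocol names no such value, and the trial is sized for pain. If chondrolysis is uncommon, the most likely result is no case in either arm. As written, that result would sit beside a stated purpose of ruling the condition out, and the stated test would return nothing that shows how little a zero in this sample excludes.

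What is at stake is the accuracy of one secondary safety statement. Cartilage exposure is part of the background rationale for choosing a capsular injection, so readers will look for that statement. The pain and narcotic comparisons do not depend on it.

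**Working it through.** **Inputs.** 60 enrolled, allocated about 1:1, so about 30 injected. 26 per arm is the planned minimum. Both come from the Methods and Power Analysis. The documents give no chondrolysis rate and no sensitivity for the clinical check, so those values below are assumptions shown as ranges.

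**The plan's own figure.** For a difference of 2, SD 2.5, two-sided alpha 0.05 and 80% power, the normal approximation gives n = 2 × (1.96 + 0.84)² × 2.5² / 2² ≈ 24.5, or 25 per arm. The exact t calculation gives 25.5, rounded up to 26. Power is 80.7% at 26 and 86.1% at 30 per arm. The stated figure reproduces, and it concerns pain only.

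**What zero cases exclude.** If the true risk is p, the chance of no case in n patients is (1 − p)ⁿ. Setting this to 0.05 gives the one-sided 95% upper limit, 1 − 0.05^(1/n). Setting it to 0.025 gives the two-sided Clopper-Pearson limit, 1 − 0.025^(1/n).

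| Injected and assessed | One-sided 95% | Two-sided exact 95% |
|---|---|---|
| 22 | 12.7% | 15.4% |
| 26 | 10.9% | 13.2% |
| 30 | 9.5% | 11.6% |
| 38 | 7.6% | 9.3% |

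The rows for 22 and 38 are the 95% range of arm size if the odd/even rule is simple randomisation without blocking, which the protocol does not specify.

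**How often a zero would occur anyway.** With n = 30, (1 − p)³⁰ gives:

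| Assumed true risk | Chance of no case in 30 |
|---|---|
| 0.5% | 86% |
| 1% | 74% |
| 2% | 55% |
| 5% | 21% |
| 10% | 4% |

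**Number needed to exclude a given rate.** Solving (1 − p)ⁿ ≤ 0.05, zero cases would be needed in 59 injected patients to exclude 5%, in 149 to exclude 2% and in 299 to exclude 1%.

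**Detection.** These limits apply to cases the three-month check would find. If it found only half of them (an assumption), the one-sided limit for 0/30 would be 9.5% / 0.5 = 19% for all cases.

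**The chi-square test.** With no case in either arm, the expected number of cases per arm is 0 × 30 / 60 = 0. Each of those cells contributes (0 − 0)² / 0, which is undefined, so the test has no value.

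With a handful of cases the test exists but is unreliable. At 4/30 against 0/30 the uncorrected statistic is 60 × (4 × 30)² / (30 × 30 × 4 × 56) = 4.29, above the 5% critical value of 3.84, while Fisher's exact test gives p = 0.112. The expected number of cases is only 2 per arm. By Fisher's test, 5 against 0 gives p = 0.052 and 6 against 0 gives p = 0.024.

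**The case against.** The strongest reply is that the protocol never claims safety. The phrase is a short parenthesis in a list, identical for the arm that gets no injection, and clinicians commonly use it to mean *check for*. The objective, hypothesis and power analysis cover pain and narcotic use only, and the Post-operative Care wording is already neutral. This largely stands. It is why the point is minor, and why the fix amounts to bringing the list into line with the later section. What remains is that the phrase sits among the study variables with nothing to confine it to the individual patient, and as a statement about the group it cannot be met.

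A second reply is that an exact interval for a secondary safety count belongs in a statistical analysis plan, which may exist but is not shown. Its absence alone would indeed be no finding. But the protocol itself fixes a method for complications, and that method fails in the most likely case.

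Three stronger readings are tempting, and the documents do not support them:

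- *A zero count will be reported as proof of safety.* A reader might infer this, but no section says so.
- *By the protocol's own account, three months is too early.* The Background says "The long term effects, including chondrolysis have been documented in the shoulder and while in the short term this effect is diminished". That sentence concerns intra-articular agents, whereas the trial studies a capsular injection. Its short-term clause could also mean short exposure rather than early follow-up.
- *The check is clinical only and therefore insensitive.* The text is "be clinically assessed for the presence of chondrolysis (a frequently measured". It specifies no imaging but does not exclude it, and no sensitivity is given.

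**Conclusion.** The point holds in a limited form. With about 30 injected patients, no case means only that the risk of clinically detected chondrolysis by three months is unlikely to exceed about 10–12% (0/30: 9.5% one-sided, 11.6% two-sided; 0/26: 10.9% and 13.2%). That does not amount to ruling the condition out. The chi-square test stated for complications gives no result if both arms have zero cases.

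The bound needs only the arm size and the assumption that patients are independent and all assessed. Missed visits or a smaller injected arm would widen it. It says nothing about later onset or about cases the check would miss. The 0.5% to 10% risks used in the working are illustrative, and the conclusion does not depend on them.

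This is a minor secondary-outcome point. It does not show that the injection is unsafe, that the investigators intend a safety claim, or that the pain comparison is weakened.

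**What to change.** - In METHODOLOGY, Variables, items 1d and 2d, replace the ruling-out phrase with *clinical screen for signs of chondrolysis at three months*.
- In Statistical Analysis, state that chondrolysis will be reported as a count per arm, over the number assessed, with an exact (Clopper-Pearson) 95% interval, instead of relying on chi-square. For 0/30 the upper limit is 11.6%.
- In the same place, limit the conclusion for a zero count to *no clinical signs seen by three months, with the stated upper limit*, and say that the trial will not claim that chondrolysis is excluded.

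This needs no added patients, visits or measurements and leaves the pain analysis as it is. The cost is a less favourable safety statement.
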